13.3 Study Termination

The study may be terminated by the investigator or the Sponsor. If, in the opinion of the investigator, clinical observations made during the study suggest that it may be unwise to continue, he or she may stop the study. A study termination by the investigator will be reported to the Sponsor.

In addition, a written statement fully documenting the reasons for this action will be submitted to the Sponsor by the investigator within 5 working days.

In the event that the Sponsor chooses to discontinue or terminate the study, appropriate notification will be given to the investigator.

If the study is terminated for any reason subjects should be withdrawn from the study in an orderly manner following the steps outlined in [Section 13.2](#).

14. ADVERSE EVENT REPORTING

14.1 Adverse Event Definitions

An **adverse event** is any untoward medical occurrence associated with the use of a drug in humans, whether or not considered test article related.

An AE (also referred to as an adverse experience) can be any unfavorable and unintended sign (e.g., an abnormal laboratory finding), symptom, or disease temporally associated with the use of a drug, without any judgment about causality. An AE can arise from any use of the drug (e.g., off-label use, use in combination with any drug) and from any route of administration, formulation, or dose, including an overdose.

A **suspected adverse reaction** is any AE for which there is a reasonable possibility that the drug caused the event. "Reasonable possibility" means there is evidence to suggest a causal relationship between the drug and the AE.

An **adverse reaction** is any AE caused by a drug. Adverse reactions are a subset of all suspected adverse reactions for which there is reason to conclude that the drug caused the event. A suspected adverse reaction implies a lesser degree of certainty about causality than adverse reaction, which means any AE caused by a drug. For the purposes of prescription drug labeling, the term adverse reaction means an undesirable effect, reasonably associated with the use of a drug that may occur as part of its pharmacological action or may be unpredictable in its occurrence.

An AE or suspected adverse reaction is considered "unexpected" if it is not listed in the Reference Product package insert or is not listed at the specificity or severity that has been observed. For example, under this definition, hepatic necrosis would be unexpected (by virtue of greater severity) if the IB Reference Product package insert referred only to elevated hepatic enzymes or hepatitis. Similarly, cerebral thromboembolism and cerebral vasculitis would be unexpected (by virtue of greater specificity) if the Reference Product package insert listed only cerebral vascular accidents. "Unexpected," as used in this definition, also refers to AEs or suspected adverse reactions that are mentioned in the Reference Product package insert as occurring with a class of drugs or as anticipated from the pharmacological properties of the drug, but are not specifically mentioned as occurring with the particular drug under investigation.

14.2 Adverse Event Details

AEs may be either spontaneously reported, observed, or elicited during questioning and examination of a subject. All AEs following the first dose of test article must be recorded on the AE eCRF. Any untoward events occurring prior to test article administration will be reported in the Medical History, unless related to a study-specific procedure. If known, the investigator should report the diagnosis of the underlying illness or disorder, rather than its individual symptoms. Subjects experiencing AEs that cause interruption or discontinuation of test article or those experiencing AEs that are present at the end of their participation in the study should receive follow-up as appropriate. AEs should be followed to resolution or stabilization (if possible) and, if they become serious, reported as serious adverse events (SAEs, see [Section 14.3](#)). If possible, the outcome of any AEs that caused permanent discontinuation or that were present at the end of the study, especially those considered by the investigator to be related to the test article, should be reported.

Information on the medical condition of subjects should begin following the subject's written informed consent/assent to participate in the study and a medical history should be taken at screening. During any wash out and baseline periods, any changes in the health of subjects should be recorded as changes in medical history unless an event occurred as a result of a study-related procedure and is unanticipated; in such cases, the event should be recorded as an AE and reported to the IRB as an "unanticipated problem" in accordance with local procedures. Other changes in subject health information becomes AE data when the subject begins dosing with the test article; therefore AE data should be collected from the date of the first dose of test article until the date of the final study visit. These data are considered treatment-emergent AEs.

The investigator will instruct the subject to report any AEs that may occur during the study. At each visit, the investigator should ask the subject, in non-directive fashion, about any change in the subject's overall health status since the previous visit.

The severity of each AE, as judged by the investigator, will be recorded on the appropriate AE eCRF and will be graded according to the following scale:

Mild - The AE is usually transient and may require only minimal treatment or therapeutic intervention. The event does not generally interfere with usual activities of daily living.

Moderate - The AE is usually alleviated with additional specific therapeutic intervention. The event interferes with usual activities of daily living, causing discomfort, but poses no significant or permanent risk of harm to the research participant.

Severe - The AE interrupts usual activities of daily living or significantly affects clinical status, or may require intensive therapeutic intervention.

The investigator must determine the relationship of the AE to the test article according to the following categories:

Related – There is a strong medical evidence to suggest that the AE is related to test article usage.

Possibly Related – There is medical evidence to suggest that the AE may be related to test article usage.

Not Related – There is no medical evidence to suggest that the AE may be related to test article usage.

The investigator should categorize the outcome of the AE according to the following categories:

Fatal - Termination of life as a result of an AE.

Not Recovered/Not Resolved - AE has not improved or the subject has not recuperated.

Recovered/Resolved - AE has improved or the subject has recuperated.

Recovered/Resolved with Sequelae - subject recuperated but retained the pathological conditions resulting from the prior disease or injury.

Recovering/Resolving - AE is improving or the subject is recuperating.

Unknown - Not known, not observed, not recorded or subject refused.

14.3 Serious Adverse Event

An event that is serious must be recorded on the AE eCRF and on the TI SAE Report Form, and requires expeditious handling to comply with regulatory requirements.

An AE or suspected adverse reaction is considered “serious” if, in the opinion of either the investigator or Sponsor, it results in any of the following outcomes:

- Death; the event must be the cause of death for the SAE to meet this serious criterion.
- Life-threatening event; an event in which the subject was at risk of death at the time of the event and not an event that hypothetically might have caused death if it had been more severe.
- Requires inpatient hospitalization or prolongation of existing hospitalization (for ≥ 24 hours).

- Persistent or significant incapacity or substantial disruption of the ability to conduct normal life functions.
- Congenital anomaly/birth defect.
- Important medical events; a medical event(s) that may not result in death, be life-threatening, or require hospitalization but, based upon appropriate medical judgment, may jeopardize the subject and may require medical or surgical intervention to prevent one of the outcomes listed in the definition above. Examples of such medical events include allergic bronchospasm requiring intensive treatment in an emergency room or at home, blood dyscrasias or convulsions that do not result in inpatient hospitalization, or the development of drug dependency or drug abuse.

Events NOT considered to be SAEs are:

- Hospitalizations for the treatment, which was elective or pre-planned, of a pre-existing condition that did not worsen; and
- Treatment on an emergency, outpatient basis, for an event not fulfilling any of the definitions of “serious” given above and not resulting in hospital admission.

AEs classified as “serious” by either the investigator or the Sponsor require expeditious handling and reporting to TI to comply with regulatory requirements. **All SAEs, whether related or unrelated to test article, must be reported as soon as possible but no later than 24 hours from when the event occurred by telephone to the Medical Monitor and, in the event that he is unavailable, to the Project Manager (see contact information below).** Written notification of all SAEs should be sent to the Project Manager by email or confirmed facsimile transmission. These include those SAEs listed in the protocol or Reference Product package insert and must include an assessment of whether there is a reasonable possibility that the test article caused the event.

Medical Monitor:

[REDACTED]
[REDACTED]
[REDACTED]
[REDACTED]
[REDACTED])

In the event the Medical Monitor is unavailable, contact the Project Manager:

[REDACTED]
[REDACTED]
[REDACTED]
[REDACTED]

If only limited information is initially available, follow-up reports are required. Should the investigator become aware of an SAE (regardless of its relationship to test article) that occurs within 30 days after stopping the test article, the SAE must be reported in

accordance with procedures specified in this protocol. In the event of death, if an autopsy is performed, a copy of the report should be sent to TI, if available.

Upon receiving such notices, the investigator must review and retain the notice with the Reference Product package insert and promptly submit a copy of this information to the responsible IRB according to local regulations. The investigator and IRB will determine if the informed consent/assent require revision. The investigator should also comply with the IRB procedures for reporting any other safety information. Where required, submission of safety updates by the investigator to Health Authorities should be handled according to local regulations.

The Sponsor or designee may be required to report certain SAEs to regulatory authorities (e.g., United States FDA) within 7 calendar days of being notified about the event; therefore, it is important that investigators submit any information requested by the Sponsor or designee as soon as it becomes available.

14.4 Laboratory Test Abnormalities

There are no specific laboratory tests, other than UPT, required in this study.

14.5 Pregnancy

WOCBP (see [Schedule of Events](#) for definition of WOCBP) must have a UPT prior to study enrollment. Prior to study enrollment, WOCBP must be advised of the importance of avoiding pregnancy during the study and the potential risk factors for an unintentional pregnancy. The subject must sign an informed consent/assent (if applicable) form documenting this discussion.

WOCBP should be instructed to contact the investigator immediately if they suspect they might be pregnant (e.g., missed or late menstrual period) during the study and for 30 days after she has completed her last test article application. If a subject or investigator suspects that a subject may be pregnant at any time during the study, the test article must be withheld until the results of laboratory pregnancy testing are available. If pregnancy is confirmed, the subject must not receive or apply further test article and the subject must be discontinued from the study.

If following initiation of study treatment, it is subsequently discovered that a subject was pregnant or may have been pregnant at the time of test article exposure, the investigator must immediately notify the Medical Monitor of this event and record the pregnancy on the appropriate pregnancy surveillance form. The form will be sent to TI. The investigator will also report any pregnancy associated with the study treatment as required by their IRB and keep careful source documentation of the event.

Protocol-required procedures for those subjects that are discontinued from the study must be performed on the subject unless contraindicated by pregnancy (e.g., x-ray studies).

Other appropriate pregnancy follow-up procedures should be considered if indicated, including counseling of the subject by the investigator and her managing physician or health care provider (e.g., obstetrician). In addition, the investigator must report to TI, on the appropriate pregnancy surveillance form(s), any follow-up information regarding the course of the pregnancy, including perinatal and neonatal outcome. Although pregnancy itself is not an AE, any complications during pregnancy should be recorded as AEs or SAEs (if they fulfill the SAE criteria). Offspring should be followed for a minimum of 8 weeks. Any congenital anomaly/birth defect in a child born to a subject exposed to the test article(s) should be recorded as an SAE with details documented in the pregnancy surveillance form. Abortion, whether accidental, therapeutic, or spontaneous should be reported as an SAE. Elective abortions are generally not reported as an SAE unless an AE occurs that meets the criteria for an SAE.

15. BLINDING/UNBLINDING

This is a double-blind, randomized, placebo-controlled study. Blinding is important for the integrity of this clinical study. Test article will be packaged in identical bottles so that neither the subject, investigator nor site staff will know the identity of the contents. However, the blind may be broken in the event of a medical emergency in a subject, in which knowledge of the test article identity is critical to the subject's management. Before breaking the blind for a subject, the investigator should determine that the information is necessary (i.e., that it will alter the subject's immediate management). In many cases, particularly when the emergency is clearly not test article related, the problem may be effectively managed by assuming that the subject is receiving active product without the need for unblinding. The need to break the blind should first be discussed with the responsible Medical Monitor if possible prior to breaking the blind and the best method to do this will be determined.

A sealed copy of the randomization scheme should be retained at the study site and should be available to FDA investigators at the time of site inspection to allow for verification of the treatment identity of each subject.

16. CLINICAL SUPPLIES

16.1 Test Article Information

Detailed information on the packaging/labeling, blinding/unblinding, storage and preparation, dispensing, accountability, etc. of the test article is included in [Appendix 3](#).

16.2 Supplies Provided by Therapeutics, Inc.

- eCRFs
- Source document draft templates
- Site regulatory binder
- UPT kits

- Weighing scales for test article
- Digital camera

16.3 Supplies Provided by Investigator

- Urine collection containers for UPTs

16.4 Supplies Provided by Gage Development Company, LLC

- Test article
- Samples for demonstration to subjects of test article application

17. STATISTICAL CONSIDERATIONS

17.1 Sample Size

Based on the assumption of a 40% reduction in inflammatory and non-inflammatory lesions counts for the Reference Product and a 38% reduction for GDC 268, 346 PP subjects per active arm will provide 85% probability of demonstrating therapeutic equivalence between the two active treatments at an $\alpha=0.05$ (two one-sided tests) with 90% confidence interval bounds of the ratio of means being 0.08 and 1.25. Assuming a 25% reduction in inflammatory and non-inflammatory lesions counts for the VEH, 231 mITT subjects in the VEH arm and 462 mITT subjects in each of the active treatment arms will provide at least an 85% probability of demonstrating that each active treatment is statistically superior to vehicle treatment at a two-sided α of 0.05. Therefore, approximately 1200 subjects will be enrolled using a 2:2:1 randomization ratio (GDC 268: Reference Product: VEH) to obtain a total of 1155 mITT subjects and 865 PP subjects.

17.2 Endpoints

17.2.1 Efficacy Endpoints

Co-primary efficacy endpoints will include:

- Percent change from Baseline to Week 12 in the inflammatory (papules and pustules) lesion count.
- Percent change from Baseline to Week 12 in the non-inflammatory (open and closed comedones) lesion count.

17.2.2 Safety Endpoints

Safety endpoints will include:

- Incidence (severity and causality) of any reported or observed treatment emergent AEs, whether or not they are considered to be related to the test article.

- Number of subjects with improved/same versus worsened severities compared to Baseline of the following LSRs: erythema, edema, scaling/dryness, stinging/burning, pruritus, erosion, and pain at each onsite treatment visit.

17.3 Statistical Methods

All statistical processing will be performed using SAS® Version 9.4 unless otherwise stated.

The Safety population will include all randomized subjects who applied at least one dose of test article.

The mITT population will include all randomized subjects who applied at least one dose of test article.

The PP population will include all mITT subjects who met all I/E criteria, were compliant with the assigned test articles based on the subject diaries (applied at least 75% and no more than 125% of the expected test article applications for the specified duration of the study), did not miss the scheduled test article applications for more than 3 consecutive days (i.e., 3 consecutive days with no test article application), have no other evidence of material dosing noncompliance, and completed the primary endpoint evaluation at Week 12 within the designated visit window (Day 85 ± 4 days) with no protocol violations that would affect the treatment evaluation including use of the prohibited medications.

Subject randomization will be stratified by the number of non-inflammatory lesions (≤ 70 / > 70) present at the Baseline Visit in order to ensure balanced enrollment of subjects across the treatment groups by non-inflammatory lesion count. No subset analyses are planned based on baseline non-inflammatory lesion counts.

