
Study Measurements
	
Dosing Compliance: Measures of test article compliance will include the duration (days) of treatment (defined as last dose date – first dose date +1), the total number of applications applied and missed (determined from the doses reported in the Subject Diary), and the percent of expected doses applied. A subject will be considered compliant with the dosing regimen if the subject applies at least 75% and no more than 125% of the expected test article applications for the specified duration of the study and does not miss the scheduled applications for more than 3 consecutive days.
 
Efficacy and safety measurements will be assessed according to the schedule of events.
 
Efficacy: Investigator’s Global Assessment Overall severity of acne will be assessed using a five-point scale where 0=Clear, 1=Almost Clear, 2=Mild, 3=Moderate, and 4=Severe. This is a static morphological scale that refers to a point in time and not a comparison to Baseline.
 
Acne Lesion Counts The number of non-inflammatory lesions (open and closed comedones) and inflammatory lesions (papules and pustules) on the face (including those present on the nose) will be counted. Counts of nodules and cysts will be reported separately and are not to be included in the inflammatory or non-inflammatory lesion counts.
 
Safety: Adverse Events All reported or observed AEs will be recorded. At each visit, subjects will also be questioned specifically about the status of any ongoing AEs. Untoward events that occur prior to the first dose of test article will be captured in the Medical History section of the electronic case report form (eCRF) unless they are related to a study-specific procedure.
 
Local Skin Reactions At each visit, LSRs (erythema, edema, scaling/dryness, stinging/burning, pruritus, erosion, and pain) will be assessed. Erythema, edema, scaling/dryness, and erosion will be assessed by the investigator and stinging/burning, pain, and pruritus will be assessed by the subject. Assessments will be made using a 4-point ordinal scale where 0=absent, 1=mild (slight, barely perceptible), 2=moderate (distinct presence), and 3=severe (marked, intense). Only LSRs that require medical intervention

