17.3.1 Dosing Compliance

Descriptive statistics will be used to summarize test article compliance for each analysis population. Compliant subjects are defined as those who apply at least 75% and no more than 125% of the expected test article applications, and did not miss scheduled applications for more than 3 consecutive days. The percentage of compliant subjects will be also presented.

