17.3.2.3 Imputation of Missing Data

Subjects who are discontinued early from the study due to lack of treatment effect after 4 weeks of treatment will be included in the PP population analyses using LOCF. Subjects whose condition worsens and who require alternate or supplemental therapy for the treatment of their condition during the treatment phase of the study will be included in the mITT and PP population analyses using LOCF. Subjects discontinued early for other reasons will be excluded from the PP population, but included in the mITT population, using LOCF.

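### LOCF for subjects who start alternate acne therapy can carry a count taken on that therapy, and the per-protocol definition omits the treatment-failure exception

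*Combined protocol and SAP*

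**What the plan says.** **Treatment failures.** Section 17.3.2.3 names two groups for the PP analyses. One is subjects discontinued early for "lack of treatment effect after 4 weeks of treatment will be included in the PP population analyses using LOCF". The other is "Subjects whose condition worsens and who require alternate or supplemental therapy for the treatment of their condition during the treatment phase of the study", who go into both mITT and PP by LOCF. It then states: "Subjects discontinued early for other reasons will be excluded from the PP population".

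**PP definition.** Section 17.3, repeated in the synopsis (Statistical Methods), admits a subject who "completed the primary endpoint evaluation at Week 12 within the designated visit window (Day 85 ± 4 days) with no protocol violations" affecting the evaluation, and it lists prohibited medication among those violations. It requires that the subject "applied at least 75% and no more than 125% of the expected test article applications for the specified duration of the study". It has no exception for treatment failures and no pointer to 17.3.2.3.

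**Missed doses.** The same definition excludes subjects who missed applications "for more than 3 consecutive days (i.e., 3 consecutive days with no test article application". The compliance definitions have no such gloss. Section 17.3.1 requires "no more than 125% of the expected test article applications, and did not miss scheduled applications for more than 3 consecutive days", and the synopsis (Study Measurements) requires that the subject "does not miss the scheduled applications for more than 3 consecutive days".

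**Context.** Section 13.2 permits but does not require withdrawal for lack of efficacy, progressive disease or protocol deviation. Lesions are counted at Weeks 4, 8 and 12 or early termination (9.3, 9.4), but the unscheduled visit (9.5) lists no count. Section 8.1 bars other acne treatments during the study. Equivalence is decided in PP and superiority over vehicle in mITT with LOCF (17.3.2.1). No sensitivity analyses are planned (17.3.2.4).

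**The concern.** A subject who worsens, starts another acne therapy and stays in the study goes on being counted. LOCF in its ordinary sense uses the latest available count, which may then reflect the other therapy. A failure of the assigned product would enter the analysis as a partial or full success.

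In the equivalence ratio this hides whatever part of the test-reference difference comes from unequal failure rates. The same rule applies in mITT, so it also reaches both vehicle comparisons: if vehicle has more failures, the vehicle mean is raised and the active-vehicle difference shrinks.

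The second problem concerns who is in PP. Taken alone, the definition in 17.3 removes subjects whom 17.3.2.3 says are included. Two programmers could build different PP sets from the same text, and PP is the set on which equivalence is decided. The missed-dose wording is a smaller instance of the same problem.

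**Working it through.** **1. Which count is carried.** For a lack-of-effect discontinuation, the early termination count gives LOCF a natural meaning. For a subject who starts alternate therapy at, say, Week 4 and stays, the candidates are Week 4 (before that therapy) and Weeks 8 and 12 (on it). The text does not choose.

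**2. The plan's own power figure.** Section 17.1 gives 346 PP subjects per active arm, reductions of 40% (reference) and 38% (test), one-sided alpha 0.05 and 85% power. I use the limits 0.8 and 1.25 from 17.3.2.1 (17.1 prints 0.08). No SD is given, so the 85% cannot be reproduced directly.

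Power is the joint probability of passing both tests (normal approximation, one endpoint, common SD):
- Lower: Φ[(mT − 0.8·mR)/(SD·√(1/nT + 0.64/nR)) − 1.645]
- Upper: Φ[(1.25·mR − mT)/(SD·√(1/nT + 1.5625/nR)) − 1.645]

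Solving for 85% at n = 346 gives SD ≈ 32.3; I use 32.5. Check: lower (38 − 32)/2.238 − 1.645 = 1.04, giving 0.850; upper (50 − 38)/2.797 − 1.645 = 2.65, giving 0.996; joint 84.6%.

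**3. Effect of the carried value (illustration).** Assume:
- 38% and 40% are the means of non-failures;
- a fraction f of each arm fails, and every failure is on alternate therapy;
- failures carry c% reduction: 0% for a count before alternate therapy, 40% for one after it.

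Then arm mean = (1 − f)·38 or (1 − f)·40, plus f·c, and n = 346/(1 − f).

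| Failures, test vs reference | Ratio, c = 0 | Power | Ratio, c = 40 | Power |
|---|---|---|---|---|
| 2% vs 2% | 0.95 | 84% | 0.95 | 86% |
| 3% vs 2% | 0.94 | 80% | 0.95 | 86% |
| 6% vs 2% | 0.91 | 64% | 0.95 | 87% |
| 2% vs 6% | 0.99 | 92% | 0.95 | 86% |

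Worked case, 6% vs 2%, n = 368 and 353:
- c = 0: means 35.72 and 39.20; lower test (35.72 − 31.36)/2.187 − 1.645 = 0.35; power 64%.
- c = 40: means 38.12 and 40.00; lower test (38.12 − 32.00)/2.187 − 1.645 = 1.15; power 87%.

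Over SD 28 to 35, the c = 0 power at 6% vs 2% runs from 75% down to 58%. Each 1% of failures moves an arm's mean by 0.01 × 40 = 0.4 points between the two choices, in the mITT vehicle comparisons too.

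The last row shows that the direction is not fixed. Carrying post-therapy counts pulls the ratio back towards 0.95, the value among non-failures. That helps equivalence when the test arm fails more often and hurts it when the reference arm does.

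**4. PP definition against the imputation rule.**

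| Condition in 17.3 | Stopped for lack of effect | Worsened, on alternate therapy |
|---|---|---|
| In-window Week 12 evaluation | Generally not met | Met only if the subject stays |
| No prohibited medication affecting evaluation | Can be met | Generally not met |
| Status in 17.3.2.3 | In PP by LOCF | In PP by LOCF |

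For compliance, the first dose is on the evening of Day 1. Full dosing to the morning of Day 57 is 1 + 55×2 + 1 = 112 applications; to the morning of Day 85 it is 1 + 83×2 + 1 = 168. A fully adherent subject stopped at Week 8 is at 112/168 = 67% over 12 weeks, or 112/112 = 100% over time on treatment. On the 12-week reading, nobody stopped before Day 64 can reach 75% (126 applications).

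**5. Missed doses.** A gap of exactly 3 days is 6/168 = 3.6% of doses, so the 75% rule does not settle it. If an assumed 1%, 5% or 10% of PP subjects had such a gap and were dropped, power would fall from 85% to 84%, 83% or 81%.

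**The case against.** The strongest reply is that 17.3.2.3 is a specific rule inside the section that holds the PP definition. It says these subjects are included and excludes only other reasons, so it governs. That stands: the intent to include is clear, and the definition lacks only the matching exception. A reader might infer that the plan drops treatment failures from PP; the documents do not support that.

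A reader might also infer that early stoppers fail compliance on a 12-week denominator. That reading would largely empty 17.3.2.3, and the synopsis lists treatment duration from first to last dose among its compliance measures. Appendix 3.6, listed in the contents but not shown, may define expected doses. The point therefore needs confirmation only.

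On the carried count, it can be argued that invoking LOCF for subjects who may reach Week 12 already implies a count taken before the other therapy. That is plausible, but the text does not say it.

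The operative words on missed doses are more than 3 days in every place; only the parenthesis differs. That limb is editorial.

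Finally, 17.3.2 provides for efficacy analyses in mITT as well as PP. This gives some view of robustness, but mITT differs from PP in many other ways, and the carried-count gap affects it too.

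**Conclusion.** The concern holds, led by the carried-forward count. As written, LOCF can attribute another therapy's effect to the assigned product, in PP and in mITT. The PP definition contradicts the inclusion of treatment failures on its face, and the missed-dose cutoff is inconsistent within one clause. All three should be settled before unblinding.

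The size is unknown. The illustration rests on an assumed SD, assumed failure rates and carried values, and all failures being on alternate therapy. With similar failure rates the carried-count choice matters little (84% to 86% at 2% in each arm); it becomes large only with a marked imbalance such as 6% versus 2%.

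A reader might infer from the 64% that the trial is underpowered. The documents do not support that: they give no failure rate and do not say whether the 38% and 40% already include failures. Nor do they support an inference that PP membership could be chosen knowing treatment, since section 7 keeps assignment blinded until database lock. This is a matter of attribution and reproducibility.

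**What to change.** Before unblinding:

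1. **Section 17.3.2.3.** State that for subjects who start alternate or supplemental therapy, the last count before that therapy is carried forward in both mITT and PP, even if later counts exist. If there is no earlier post-baseline count, use Baseline (0% change).
2. **Section 17.3 and the synopsis.** Write the treatment-failure exception into the PP definition, covering the Week 12 window and disqualification for that therapy. Confirm that these subjects' compliance is judged over time on treatment, unless Appendix 3.6 already defines expected doses.
3. **Missed doses.** Reconcile the wording to one cutoff in both synopsis entries, 17.3 and 17.3.1. Which cutoff is for the sponsor to decide.

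The rules in item 1 and the compliance basis in item 2 are suggestions; the visible text does not contain them.

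The cost is wording only, with no new data, provided the start date of the alternate therapy is captured with the concomitant-medication changes that section 8 requires. Mean reductions may be slightly less favourable than with post-therapy counts. Because 9.5 lists no lesion count, the carried count may be some weeks old when therapy starts between scheduled visits.
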